Re: Therapy and ketamine trial-- Participants are not randomized. They will be fully informed of the free therapy and ketamine trial and will not be coerced into it. Free therapy and ketamine will be provided to all patients (as this is a feasibility and acceptability study). If any patient participating in the study needs a higher level of care, they will immediately be removed from the treatment protocol and will be coordinated with other providers to ensure they get the care necessary. If any patient participating in the study decides they no longer want to be in the trial, they can end at any point and it will be coordinated to help them continue treatment with other providers.

Re: experimental session—all participation is voluntary, including answering questions and participating in the ERP.

2.c Subject Recruitment Plans and Consent Process

Study population:

Young adults age 18-65 years with TRD who exhibit HPM/OC.

Consent process: If an interested participant contacts the research team about the study, a member of the research team will provide information about the study and required elements of consent over the telephone (see attached “Consent for Phone Screen”) prior to obtaining the participants verbal consent to participate in the screening elements of the study. This phone screen will allow possible participants to ask questions and clarifications prior to coming in person for the in-person consent process (and includes the child having the opportunity to ask questions). If a participant meets eligibility criteria for enrollment in the study based on their Initial Phone/Exclusion Screen and the participant indicates they wish to continue with the study, the participant will receive an email to complete the a measure of HPM/OC, the Word Pairs Checklist. The participant must consent to complete these questionnaires. If the participant is eligible following completion of the phone screen and questionnaires, the research team will notify the participant of their eligibility and ask whether they want to continue with the study. If the participant is unsure, the research assistant will provide

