unlimited time for the participant to consider whether they would like to participate in the study and a research assistant will notify the participant they can contact the research team if they would like to potentially participate in the future (they may have to re-complete the phone screen at that future time). If the person is still interested, the research team will schedule an in-person session.

The consent process will take place in person at Washington University in St. Louis Department of Psychiatry in a private room with a research team member. The consent process will include providing ample time for the young adult to read/review the consent form. This consent will consent for the experimental sessions and the free ketamine and therapy portion. There is no randomization: if an potential patient participant is interested in the free ketamine/therapy, they can participate in that until we have 15 participants in the therapy portion. A trained research assistant will also discuss the procedures of the study and will answer any questions the participant may have prior to signing. Research team members will remind participants that their participation is completely voluntary and they can choose to withdraw at any time.

2.d Early Withdrawal of Subjects

Participants can withdraw at any point if they desire. Participants in need of higher levels of care will be withdrawn by the PI if medically/psychologically unstable or if they express active suicidal ideation.

2.e When and How to Withdraw Subjects

Participants in need of higher levels of care will be withdrawn by the PI at any point if medically/psychologically unstable or if they express active suicidal ideation and need to be hospitalized. If a participant desires to withdraw, as soon as they inform the study team, the team will remove the participant from current and future study procedures.

2.f Data Collection and Follow-up for Withdrawn Subjects

Data will not be collected for withdrawn subjects once they withdraw. Follow-up for withdrawn subjects will not be done, unless the patient reaches out to us and would like to continue the therapy or study. At this point they would sign another consent form to agree to their continued participation.

F Study Procedures

F1 Screening for Eligibility

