Clinicians will be [name], BA, [name], MA, LPC, [name], MSW, LCSW, [name], MA, LPC and [name], MA. [name], [name], [name] and [name] are all licenced therapists in the St. Louis community and [name] is a PhD clinical psychology graduate student in the Department of Psychology at Washington University. All clinicians have been intensively trained in RO DBT. Group skills classes will be run by both the PI, [name], [name] and/or another clinician. Paper notes will be kept in a locked file cabinet in locked offices. De-identified therapy notes will be uploaded to a secure Wustl box.com folder for the study. At the end of therapy, the clinician will complete an “End of Therapy Progress” questionnaire to assess progress made or not made across the research study. In addition, the participant will be contacted via phone call and asked several questions about their experience with RO DBT along with their perceptions of treatment outcomes. In addition, research team member will contact subjects who have dropped out of the study or who have completed treatment. The participant will be contacted via phone call to and invited to participate in a follow up interview. They will be asked several questions about their experience with

Ketamine enhanced RO DBT along with their perceptions of treatment outcomes. This will be conducted over zoom and be recorded or over the phone and audio recorded to a handheld recorder. The recording will be immediately transferred to a wustl box, in a secured password protected account. The data from the recording will be deleted immediately from the handheld recorder. At the end of the study a research team member will transcribe the recordings and save the transcriptions to a wustl box folder. All audio and video recordings will be deleted at that time.

G Statistical Plan

G1 Sample Size Determination and Power

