H2a: Ketamine-enhanced RODBT will be associated with neural ERN reductions and neural RewP increases. Analysis 2a: Using baseline, mid- and post-treatment assessments, change in the ERN (and in a separate model, the RewP) will be assessed using a MLM. **H2b:** Ketamine-enhanced RODBT will be associated with behavioral cognitive flexibility, openness, reward responding and social functioning improvements. Analysis 2b: Using baseline, mid- and post-treatment assessments, change in behavioral mechanisms will, similar to Analysis 2a, be assessed using a MLM.

G4 Statistical Methods

See above

G5 Missing Outcome Data

If missing outcome data exists, that participant will be excluded for that analysis. Of note, when modeling data, missing data does not mean the participant can be excluded.

H References

1. Lynch TR. Radically Open dialectical behavior therapy: Theory and practice for treating disorders of overcontrol. Oakland, CA: Context Press; 2018.

-

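### Section 2.f stops outcome collection for participants the PI withdraws because they deteriorate, and it conflicts with the planned contact of dropouts

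*Combined protocol and SAP*

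**What the plan says.** Section 2.b (Ethical Considerations) covers any patient who "needs a higher level of care, they will immediately be removed from the treatment protocol", and arranges care with other providers. Section D1, under the risks of RODBT, names declining mental status as a reason to step a participant up to higher care. Under 2.d, participants in need of higher care "will be withdrawn by the PI if medically/psychologically unstable or if they express active suicidal ideation". Section 2.e repeats this with a narrower condition on ideation: "if they express active suicidal ideation and need to be hospitalized".

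Section 2.f sets the consequence: "Data will not be collected for withdrawn subjects once they withdraw", and "Follow-up for withdrawn subjects will not be done, unless the patient reaches out to us" wishing to continue, in which case a further consent form is signed.

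Section F (Therapy) says that a "research team member will contact subjects who have dropped out of the study or who have completed treatment", inviting them to a recorded interview about their experience and how they see their outcomes.

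The planned outcome visits are baseline, mid-treatment (after ketamine) and post-treatment, the last two with the same ERP and questionnaire content as the first (section F). The questionnaires include the PHQ-9. Section G3 uses multilevel models (MLMs) for depressive trajectories (Analysis 1b), ERN and RewP (2a) and behavioural mechanisms (2b). On missing data, G5 says: "If missing outcome data exists, that participant will be excluded for that analysis", and then: "when modeling data, missing data does not mean the participant can be excluded".

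**The concern.** The plan does not clearly separate stopping treatment from leaving the study. A participant taken off treatment for clinical decline may be willing and able to attend the later assessments, but nothing in the plan invites them. The missing outcomes are then not a random subset: they belong to participants selected for doing badly. With no control group and 15 participants, a few such cases could shift the estimated change in the favourable direction.

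There is also an operational conflict. For someone who has left, 2.f tells staff to wait for the patient to make contact, while section F tells them to initiate it.

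**Working it through.** **Step 1. Trace the route.** Decline leads to step-up in care (D1), removal from treatment (2.b), withdrawal by the PI (2.d, 2.e), and no further data or follow-up (2.f). The two sections directly above 2.f describe people withdrawn by the PI. Section 2.f is headed for withdrawn subjects generally and exempts none of them.

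**Step 2. Data lost per removal.** Three assessments are planned.
- Removed before the mid-treatment visit: 3 − 1 = 2 of 3 lost.
- Removed between mid- and post-treatment: 3 − 2 = 1 of 3 lost.
- Each participant is 1/15 = 6.7% of the sample.

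**Step 3. Effect on each analysis.**
- *1b:* Session PHQ-9 scores end with the sessions in any case. What 2.f adds is loss of the PHQ-9 at the mid- and post-treatment visits.
- *2a and 2b:* A participant removed before the mid-treatment visit has a baseline value only, which says almost nothing about change. The models as described do not include the PHQ-9 course that led to removal. The direction of any bias here depends on clinical decline going with less change in the target, a link the study itself sets out to test (B1).

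**Step 4. Illustration of size, on assumed inputs.** The plan states no removal rate or expected PHQ-9 change, so there is no figure of its own to reproduce.

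*Completers only.* Let w be the share removed, s the mean change of those who stay and d that of those removed. The true mean is (1 − w)s + wd, so a completers-only mean overstates improvement by w(d − s). Assume s = −6 points and d between 0 and +4, so d − s is 6 to 10.

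| Removed of 15 | Overstatement (points) |
|---|---|
| 1 | 0.4 to 0.7 |
| 2 | 0.8 to 1.3 |
| 3 | 1.2 to 2.0 |
| 4 | 1.6 to 2.7 |

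*Multilevel model keeping data before removal.* The simulation had 15 participants and weekly scores over weeks 0 to 18. The starting mean was 17 (SD 3), the slope −0.35 per week (SD 0.3) and the residual SD 2. Each participant had a 20% chance of removal between weeks 3 and 14, with a lasting worsening that starts at removal. There were 100 replicates, all of which converged, with standard errors of 0.13 to 0.17.

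| Worsening at removal | True mean change | MLM, collection stops | MLM, collection continues |
|---|---|---|---|
| 0 | −6.5 | −6.4 | −6.4 |
| 4 | −5.6 | −6.4 | −5.3 |
| 8 | −4.7 | −6.4 | −4.2 |

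With stopping, improvement is overstated by 6.38 − 5.59 = 0.79 and 6.38 − 4.70 = 1.68 points, close to 0.2 × 4 = 0.8 and 0.2 × 8 = 1.6. With no worsening, the two rules agree with the truth within simulation error. Two limits apply. The worsening begins exactly when data stop, which is the case least favourable to 2.f. The continuing arm keeps weekly scores, which is more than the two planned visits would supply, and a straight line fitted to a step understates improvement by 0.28 and 0.48 points.

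**Step 5. Set 2.f beside section F (Therapy).** One bars follow-up unless the patient initiates it; the other has staff initiate it. The protocol defines neither withdrawn nor dropped out, so no stated distinction reconciles them. The interview covers experience and perceived outcomes; no PHQ-9 or EEG is mentioned, so it would not replace the endpoints.

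**The case against.** **Section 2.f may mean self-withdrawal only.** Its verb fits the participant's own act, and 2.b removes people from treatment while addressing the experimental session separately. This stands as a possible reading and is why confidence is moderate. The heading of 2.f and the PI withdrawals described just above it point the other way.

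**A reader might infer that these outcomes are irretrievably lost.** The text does not go that far: a patient who makes contact can rejoin the therapy or the study under new consent. What is missing is an invitation from the study team.

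**A reader might infer that G5 also discards scores from before removal.** Its first sentence taken alone would do so. But every inferential analysis in G3 is an MLM and the second sentence is specific to modelling, so the natural reading keeps those scores. Frequent PHQ-9 collection may also record part of a decline before removal. Neither helps with worsening that falls at or after removal.

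**Scores after removal answer a different question.** Analysis 1b concerns trajectories across treatment, and later scores reflect other care too. This is fair. It argues for recording when other care began and interpreting those scores accordingly, not for leaving the outcomes unknown.

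**A reader might see a safety gap in the differing suicidality conditions of 2.d and 2.e.** The documents do not support that: 2.b stops treatment whenever higher care is needed, and both clauses concern participants who need such care. The difference has no stated effect on any analysis. Aligning the two is an editorial clean-up outside this point.

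**Conclusion.** The point holds. As most naturally read, 2.f means the study does not seek mid- and post-treatment outcomes from participants the PI withdraws for deterioration, so missingness depends on poor outcome. The separate conflict with section F over who may initiate contact is plain on the text.

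No bias of a particular size can be claimed. Overstated improvement in depressive symptoms requires that removals occur and that worsening coincides with removal without already showing in earlier scores. For the neural and behavioural targets it also requires the untested link between decline and target change. The illustrative figures show how the mechanism works under assumed inputs; they are not forecasts.

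Severity is minor: this is a 15-person, single-arm feasibility study, and the remedy is a wording change. Confidence is moderate because the narrower reading of 2.f cannot be excluded.

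**What to change.** 1. State in 2.b, 2.d and 2.e that removal from treatment by the PI does not end study participation. Invite the participant to the mid- and post-treatment assessments already planned, including the PHQ-9, when clinically safe, unless they withdraw consent for assessments.
2. Record the date of removal and the start of other care.
3. Limit 2.f to participants who withdraw consent for assessments, and name the section F interview as permitted contact unless refused.
4. State in G5 that all available data from removed participants stay in the MLMs, consistent with its second sentence.

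The cost is a protocol wording amendment with matching consent text, and at most two already planned visits per affected participant. The downside is that scores after removal mix the study treatment with other care, so reports should identify them.

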The experimental research measures in this project will not directly benefit the participants, other than the knowledge that they are contributing to our understanding of the underlying factors that may cause treatment-resistance to previous treatments and may provide insight into a novel medication-enhanced psychotherapy and thus, there is a benefit of contribution to society. In the therapy portion of the project, it is also possible that participants may experience improved symptoms of depression, mood, anxiety, as well as reduced tendencies of HPM/OC. As part of the ketamine treatment, participants may also experience improved symptoms of depression and anxiety. There is a possible effect that the combination of ketamine and RO DBT will be especially beneficial in combination, although this is unknown, as it is a goal of the study to test the combined treatment. As mentioned above, measures are being taken to minimize any potential risks.

E Study Design

E1 Overview or Design Summary

Eligible patient (n=15) young adults will attend a baseline session where they will undergo an ERP neural assessment and fill out questionnaires. Then, participants will complete 4 weeks of ketamine and 4 months of RO DBT. Participants will start with 2 weeks of individual therapy (RODBT) to orient to therapy and infusion protocols. Then, participants will complete a 4-week course of twice weekly 40-minute ketamine infusions administered 6-24 hours prior to RO DBT psychotherapy (also when RO DBT group therapy will commence). Following completion of the 4-week ketamine-enhanced RO DBT, participants will complete another in-person session with an EEG and behavioral assessment. Next, participants will continue to complete RO DBT treatment of individual and group treatment for an additional 16 weeks. At the end of this treatment, participants will complete a third session where they will undergo an ERP neural assessment and fill out questionnaires. Participants will also complete self-reported questionnaires following each ketamine and RO DBT

session (4 weeks) and weekly self-reported questionnaires during non-ketamine RO DBT.

E2 Subject Selection and Withdrawal

2.a Inclusion Criteria

Young adults with treatment-resistant depression: Inclusion criteria:

- Males and females aged 18-65

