choose a door and the doors will remain on the screen until the participant chooses a door. Then a fixation mark is presented, followed by a feedback arrow: a green upward facing arrow indicates a correct guess (i.e., they won points), while a red downward facing arrow indicates an incorrect guess (i.e., they lost points). A fixation mark is then presented and then a screen that states, "Click for next round" is presented until a response is made. Behavioral responses will be recorded and EEG will be recorded during the task and used to measure the RewP. Participants will complete 6 minutes of resting state EEG where they will keep their eyes closed for 1 minute, followed by eyes open for 1 minute, for 6 consecutive minutes where they will be told to 'do nothing.' In total, the ERP portion of the task will take approximately 1.5 hours.

Following the ERP/EEG session, participants will meet with a researcher and complete a structured clinical interview, the Montgomery and Asberg Depression Rating Scale (MADRS) to assess current depressive symptoms. Participants will also complete the Mini International Neuropsychiatric Interview (MINI) as part of this clinical interview as well. This should take approximately 30 minutes.

Participants will then sit at a computer and complete online questionnaires on REDCap. Questionnaires will take approximately 20 minutes and can be completed at home as well. Questionnaires include:

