way) to 4 (almost always respond in this way) scale that assesses emotion regulation specifically during positive emotional experiences. The RPA has three factor-derived subscales, including Emotion-focused and Self-focused positive rumination and Dampening, which assesses ways positive emotion might be diminished (e.g., “Think about things that could go wrong”). The two positive rumination subscales are often studied in the context of bipolar disorder and are associated with elevated manic symptoms, while elevated dampening has been associated with both current and predictive depressive symptoms in both mood disordered (bipolar and depressed) and non-clinical populations (Johnson, McKenzie & McMurrich, 2008). In the current study we are using the Dampening eight item subscale only. Ask Suicide-Screening Questions (ASQ)- The ASQ is a brief (5 questions) assessment to gauge suicide risk in participants. OC Trait Rating Scale – This scale assesses maladaptive aspects of the HPM/OC 'overcontrolled phenotype' that we will use to assess whether ketamine and RO DBT are targeting the mechanistic processes inherent in the overcontrolled phenotype.

Ketamine session questionnaires:

In addition to completing the above mentioned PHQ-9 and GAD-7 at each ketamine infusion, participants will also complete:

Brief Psychiatric Rating Scale- positive (psychotic) symptoms subscale (BPRS+): This measures transient neuropsychiatric changes that might occur in response to the ketamine infusions. KetRO Clinical Events Checklist: This measure assesses common adverse side effects of using ketamine. Clinical Administered Dissociative State Scale (CADSS) – Modified – This measure assesses dissociative symptoms after using ketamine.

Before the ketamine administration, participants will have vital signs collected in addition to and ECG and blood chemistry tests.

During the ketamine + RO DBT portion of the study, participants will also complete the PHQ-9 and GAD-7 following each RO DBT session. Following completion of the ketamine portion, and ongoing weekly RO DBT therapy, participants will complete the PHQ-9 and GAD-7 weekly following their individual therapy sessions.

At the end of treatment, participants will be asked to complete a post-treatment questionnaire. The participants' therapists will also be asked to complete a separate end of therapy questionnaire.

Visit 2 etc.

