The mid-treatment (post-ketamine) and post-RO DBT treatment in-person assessments will include the identical ERP and questionnaire data.

Ketamine protocol:

Participants will be admitted to the Washington University Clinical Trial Research Unit (CTRU) to receive 0.5mg/kg intravenous ketamine given over 40 minutes, as is routinely done in ketamine treatment.(16) Participants will have same-room observation during and 1hr post-infusion to monitor blood pressure, oxygen saturation and to manage psychotomimetic adverse events by highly trained medical support staff. Side effects will also be monitored (e.g., light-headed, “high,” exhilarated, perceptual changes, hallucinations, nauseated). If a participant is unable to receive IV ketamine (e.g., because of lack of IV access), he or she can receive IM ketamine as a bolus. The dosage will be the same (0.5 mg/kg) because its bioavailability is 93% and its plasma half-life is similar to IV. We will also use clonidine as needed, taken orally the night prior to or morning of infusion to prevent distressing symptoms. Ketamine is completely cleared from the body 15 hours later; thus, key personnel have deemed that infusions will take place 1-2 days prior to RODB T individual/group sessions to maximally enhance the plasticity and potentially catalyzing effects of ketamine on psychotherapy sessions.

Therapy:

RO DBT therapy includes attending weekly one hour therapy and weekly 1.5 hours skills class sessions for approximately 16 weeks. These weekly individual therapy sessions (but not skills class sessions) will be videotaped uploaded to the WUSTL Box.com website, which is secure and encrypted. Up to 15 participants can participate in this option. RO DBT helps individuals with HPM/OC relax rigid and extreme inhibitory control, be receptive and open to new experiences and feedback and increasing social connectedness by activating the social safety system. RO-DBT treatment themes include: 1) hyper-detail-focused and overly cautious behavior, 2), rigid and rule governed behavior 3) inhibited and disingenuous emotional expression 4) distant and aloof social connectedness and relationships and 5) high social comparisons and envy.

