Using G*Power, power for Aim 1 (MDD symptoms) was based on a) a pilot of RODBT from the PI, b) Lynch et al. (2020),⁽⁹⁾ a multi-site RCT of RODBT in TRD and c) Zarate et al (2006)⁽³⁷⁾, an original RCT of ketamine in TRD. With $\alpha=.05$ and power of 80%, we would need a sample of 8 to detect an effect from RODBT, and $n=5$ with ketamine. For Aim 2, we used a) Baudinet et al (2021)⁽¹¹⁾ who tested RODBT change in behavioral flexibility and reward processing and b) a pilot of RODBT from the PI. With $\alpha=.05$ and power of 80%, we would need a sample of 5-15 participants to detect behavioral change in mechanistic process. Power for neural change in HPM/OC has not been computed because no previous studies have targeted HPM/OC with ketamine. However, our sample is similar to other medication-assisted psychotherapy pilot studies.

G2 Interim Monitoring and Early Stopping

This is part of Analysis 1a below. Specifically, side effects and symptoms will be monitored at each ketamine and RO DBT session for 4 weeks while they are running concurrently. If there are any issues with running a ketamine session and a psychotherapy session within 1-2 days of each other, protocols can be modified or stopped, if necessary.

G3 Analysis Plan

Analysis 1a: No analyses will be completed for H1a; qualitative data from session questionnaires regarding side-effects, symptoms and functioning will be continually monitored, to assess if there is a need to modify protocols. **H1b:** Using individual session data, ketamine will catalyze psychiatric symptom change in RODBT and ketamine-enhanced RODBT will be associated with decreasing trajectories of depressive symptoms. Analysis 1b: Multilevel linear modeling (MLM) with random intercepts and slopes will model trajectories of depressive symptoms across treatment.

Aim 2: Examine preliminary efficacy of ketamine-enhanced RODBT in engaging neural and behavioral mechanistic targets in young adults with

moderate to severe depression.

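### After the ketamine block, the weekly PHQ-9 and GAD-7 are timed to individual therapy sessions with no rule for missed weeks, so scores may be lost in a way Analysis 1b cannot correct

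*Combined protocol and SAP*

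**What the plan says.** The combined protocol and SAP schedules the PHQ-9 and GAD-7 in four places.

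- **Assessment visits.** Both scales are in the Visit 1 battery (F2). Under Visit 2, the mid-treatment and "post-RO DBT treatment in-person assessments will include the identical ERP and questionnaire data".
- **Ketamine block, infusions.** F2 has the "PHQ-9 and GAD-7 at each ketamine infusion". E1 makes that twice a week for four weeks.
- **Ketamine block, therapy.** F2 adds that "participants will also complete the PHQ-9 and GAD-7 following each RO DBT session".
- **After the ketamine block.** F2: "participants will complete the PHQ-9 and GAD-7 weekly following their individual therapy sessions". E1 describes the same phase as "weekly self-reported questionnaires during non-ketamine RO DBT", with no mention of attendance.

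No section says what happens to the form in a week without a session. The user of the series is Analysis 1b in G3: "Multilevel linear modeling (MLM) with random intercepts and slopes will model trajectories of depressive symptoms across treatment". G3 does not name the scale. PHQ-9 is the only depression measure listed at sessions, so I take it to be the outcome. G5 has two sentences on missing outcome data that pull in different directions, and it plans no sensitivity analysis.

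**The concern.** In the post-ketamine phase the F2 wording makes the therapy session the occasion for the form. A participant who is still enrolled but does not attend then has no scheduled PHQ-9 that week. Nothing else fills the gap until the post-treatment assessment.

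A multilevel model fitted by likelihood copes with missing weeks when the chance of missing depends on scores already observed. It does not cope when the chance depends on the unseen score of the missed week itself. Low mood in a given week is a plausible reason for not attending in that week.

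At stake is Hypothesis 1b, the efficacy statement of Aim 1, which predicts decreasing trajectories of depressive symptoms. There is one non-randomised group of 15, so no comparator would share and cancel such a bias. Scores not collected at the time cannot be recovered later.

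**Working it through.** The plan gives no attendance rate, missing-data rate or PHQ-9 SD, so it has no figure of its own to reproduce here. The sample sizes in G1 do not enter. Every input below except the schedule is an assumption, shown as a range.

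**Step 1: where the gap is.** In the ketamine block a missed therapy session still leaves up to two infusion scores that week. At baseline, mid- and post-treatment the scales are taken regardless of sessions. The gap is therefore confined to the weekly series after the ketamine block.

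**Step 2: bias in level.** Let e be a person's deviation from their own trend in a given week, normal with mean 0 and SD s. Let the log-odds of missing rise by ln(OR)/3 per point of e:

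P(miss | e) = 1 / (1 + exp(-(a + e·ln(OR)/3))), with a set to give the chosen attendance.

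The bias in the observed mean is E[e | attended], found by Gauss-Hermite quadrature (PHQ-9 points; negative looks better):

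| Attendance | s = 2, OR = 1.5 | s = 3, OR = 2 | s = 4, OR = 3 |
|---|---|---|---|
| 95% | -0.03 | -0.10 | -0.26 |
| 85% | -0.08 | -0.29 | -0.69 |
| 75% | -0.13 | -0.48 | -1.09 |
| 65% | -0.19 | -0.66 | -1.49 |

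Hand check of the central case at 85%: for weak dependence the bias is about -(ln 2 / 3) × 3² × 0.15 = -0.231 × 9 × 0.15 = -0.31, close to -0.29.

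**Step 3: change in raw means if attendance falls from 95% to 65%.** Subtract the first row from the last: -0.19 + 0.03 = -0.16; -0.66 + 0.10 = -0.56; -1.49 + 0.26 = -1.23. That is about -0.2 to -1.2 points.

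**Step 4: the planned type of model.** Raw means are not what Analysis 1b estimates, so weekly scores over 16 weeks were simulated and fitted with random intercepts and slopes. Further assumptions: intercept SD 4, slope SD 0.2 per week and, in most runs, autocorrelation 0.3. Monte Carlo error is about 0.05. Bias in the 16-week change:

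- Constant attendance, absence tied to that week's deviation: about 0. The level is shifted but the slope is not.
- Attendance falling from 95% to 65%: -0.12 to -1.12 across the same range of s and OR, with central values of -0.52 and -0.66 in separate runs.
- The same fall with the first and last scores always observed, standing for the mid- and post-treatment assessments: -0.09 to -0.79, central about -0.3.
- Absence tied to the current total score (20% of weeks missed, OR 2 or 4 per SD): -0.10 to +0.31, so the decline can be understated.
- Absence tied to the previous week's score, same settings: -0.11 to +0.10.

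For scale, the standard error of the 16-week change with 15 participants is about 1.0.

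**Step 5: after the change.** With forms sent every week and 5% missing at random (assumed), the bias is -0.01 in the 16-week change and +0.02 in the starting level.

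E1 gives 16 further weeks after the ketamine block, while the Therapy paragraph in F2 gives about 16 weeks of RO DBT in all. The two must be reconciled because they set the number of weekly points. The raw-mean figures in Steps 2 and 3 do not depend on that number.

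**The case against.** The strongest reply is that a reader could infer far more than the text supports.

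- **That the scales are collected only after attended therapy sessions.** They are not. Infusion visits and three assessments also collect them, so the point fails for the ketamine block. This objection stands in full.
- **That a skipped session means no form.** F2 may only be stating frequency and usual timing, and E1 says weekly without condition. This stands in part: the documents never say the form is dropped, but they never say it is sent either. E1 leaves an ambiguity and is not a safeguard.
- **That trajectories will look better than they are.** The documents give no attendance data and no reasons for absence. With constant attendance the slope bias is about 0, and under one mechanism it can reverse. A sizeable slope bias needs severity-related absence together with attendance that falls, or dependence that strengthens, over the course. This stands: the direction is conditional.
- **That a fixed-weekday series should become the Analysis 1b outcome.** Hypothesis 1b rests on individual session data and asks whether ketamine catalyses change around sessions. Replacing the session series would lose the alignment with infusions and sessions. This stands, and the remedy below adds scores without replacing any.
- **That answering just after seeing an unblinded therapist is part of the problem.** The study is open and single-arm, and a weekly mailing blinds nobody. It is not part of this point.

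What survives is the missing rule for a missed week after the ketamine block, and a model that does not correct absence tied to the unseen score.

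**Conclusion.** The point holds for the post-ketamine phase, and conditionally. F2 read literally loses the PHQ-9 and GAD-7 in missed weeks, E1 does not settle the matter, and the Analysis 1b model does not repair absence that depends on the current, unseen score.

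Under the stated assumptions (within-person SD 2 to 4, odds of missing 1.5 to 3 per 3 points), the level is too low by about 0.1 to 0.7 points at 85% attendance. Because the baseline is taken at a visit, that shift can add to an apparent drop from baseline; this last step is inferred and was not simulated. Within the phase, the bias in the 16-week change is about 0 at constant attendance. With attendance falling from 95% to 65% it is roughly -0.2 to -1.2 points, or roughly -0.2 to -0.7 with the mid- and post-treatment scores included. The mildest simulated cases come out nearer -0.1, and the most severe with those scores included nearer -0.8.

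The central values are below the standard error of about 1.0 for 15 participants. For a single-arm pilot of this size it is a minor-to-moderate point. It is worth acting on because the change is cheap and the lost scores cannot be recovered.

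**What to change.** 1. Reconcile E1 and F2 so that the PHQ-9 and GAD-7 go every week, for example by REDCap link, to everyone still enrolled, including weeks with no session.
2. Keep the session- and infusion-linked scores for the session-level question in Hypothesis 1b.
3. Enter all scores with their dates in Analysis 1b, with an indicator for session-linked or not.
4. Record attendance each week, and report mean scores for attended and missed weeks, so that the assumption made here can be checked.

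**Cost.** A schedule change, a few reminder contacts, and a mix of session-linked and other scores that the model must flag. F2 already has the visit battery on REDCap and says of it: "Questionnaires will take approximately 20 minutes and can be completed at home as well". It does not say this of the weekly forms, so home completion of those needs to be written in.
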